3 INVESTIGATIONAL PLAN

3.1 Study Endpoints

3.1.1 Primary Endpoint

The primary endpoint of this study is the PK profile of *Wilate*.

The PK profile is based on the following baseline PK parameters for FVIII:C using both the chromogenic (CHR) and one-stage (OS) assays and actual IMP potencies:

- Area under the curve (AUC) and AUC normalized for the administered dose (AUC_{norm})
- In vivo half-life $(T_{1/2})$
- Maximum plasma concentration (C_{max})
- Time to reach maximum plasma concentration (T_{max})
- Mean residence time (MRT)
- Volume of distribution (Vd)
- Clearance (CL)
- Incremental in vivo recovery (IVR)

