4.1.2 Inclusion Criteria

Patients who meet all of the following criteria are eligible for the study:

- 1. Severe hemophilia A (<1% FVIII:C) according to medical history
- 2. Male patients aged 1 to <12 years
- 3. Previous treatment with a FVIII concentrate for at least 50 exposure days (EDs)
- 4. Immunocompetence (CD4+ count >200/μL)
- 5. Voluntarily given, fully informed written and signed consent obtained by the patient's parent(s) or legal guardian and, depending on the children's developmental stage and intellectual capacity, informed assent by the patients before any study-related procedures are performed

The interval between the Screening Visit and the PK Visit **should not exceed 30 days**. If the 30-day interval is exceeded, determination of the CD4+ count is to be repeated and must be $>200/\mu$ L for patients to be enrolled (i.e., inclusion criterion no. 4).

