6.1.2 PK Visit

Patients will receive *Wilate* at a dose of 50 ± 5 IU/kg (labelled dose) after a washout period of at least 72 hours from their last FVIII injection. Patients must not be experiencing any bleeding.

The following assessments will be performed:

- Body weight before injection
- Blood samples will be taken for the following purposes and at the following time points:
 - FVIII:C plasma concentration (OS and CHR) for PK assessment within 1 h before injection and 15±5 min, 1 h (±5 min), 6 h (±30 min), 24±2 h, and 48±2 h after the end of injection
 - Safety laboratory before and 48±2 h after injection
 - **FVIII inhibitor** before injection
 - Plasma VWF:Ag and VWF:Ac within 1 h before injection and 15±5 min after the end of injection
- Vital signs before injection as well as 1 h (±5 min) and 48±2 h after injection
- AE monitoring
- Concomitant medications

At the end of this visit, patients will **receive a patient diary**. The Investigator will explain to the patient how to fill in the diary and emphasize the importance of carefully documenting all treatment details, AEs, and concomitant medications. Also, patients will be **provided with IMP** for home treatment. They will be re-supplied whenever necessary during the study.

The first prophylactic injection of *Wilate* after the PK Visit marks the beginning of the Prophylactic Treatment Phase.

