9.2.2 PK and Efficacy Analysis Plan

Pharmacokinetic Analysis

The analysis of the pharmacokinetic profiles of Wilate will be based on the FAS and the PP set.

The following PK parameters for FVIII:C will be analysed both for the chromogenic (CHR) and one-stage (OS) assays and actual IMP potencies:

- Area under the curve (AUC) and AUC normalized for the administered dose (AUC_{norm})
- In vivo half-life $(T_{1/2})$
- Maximum plasma concentration (C_{max})
- Time to reach maximum plasma concentration (T_{max})
- Mean residence time (MRT)
- Volume of distribution (Vd)
- Clearance (CL)
- Incremental in vivo recovery (IVR)

FVIII:C will be measured in the vials used for PK injections as well as in plasma using the CHR and OS assays.

- AUC of Wilate will be calculated from FVIII:C plasma levels measured at predefined time points and normalized for the administered dose (AUC_{norm}) using actual IMP potencies.
- All other PK parameters will be calculated from FVIII:C plasma levels measured at predefined time points using actual IMP potencies.
- Incremental IVR will be calculated from FVIII:C plasma levels measured before injection and peak levels obtained in the 15-min post-injection sample using actual IMP potencies.

The PK profiles of *Wilate* and the PK parameters derived from them will be summarized by descriptive statistics as well as the presentation of concentration vs. time plots.

For all patients, the results of the IVR assessments over time will also be analyzed in summary tables for each time point and their differences to baseline along with 95% CIs for the mean differences.

Analysis of variance (ANOVA) will be used in an exploratory sense to assess a possible association between AB0 blood type, VWF:Ag, and the FVIII:C half-life of *Wilate*.

Efficacy of Prophylactic Treatment with Wilate

Primarily, all obtained data on treatment characteristics (IMP dosages, frequencies, total consumption) and BEs (duration, frequency, efficacy assessment) will be described by providing summary statistics.

The efficacy of prophylactic treatment with *Wilate* will be statistically evaluated by presenting descriptive sampling statistics for the TABR and SABR, along with an exploratory 95% CI for the mean.

Efficacy in the Treatment of Breakthrough BEs

To assess the hemostatic efficacy of *Wilate* in the treatment of breakthrough bleedings, a frequency distribution of all such BEs being successfully treated will be presented, along with an exploratory 95% CI.

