5.8 Pharmacokinetics / Pharmacodynamics

For Pharmacokinetics and IVR assessments FVIII:C will be measured by both, the chromogenic (CHR) and one-stage assay (OS) and analyzed based on actual IMP potency (refer to section 8.1).

The PK profiles of *Wilate* and the PK parameters derived from them will be summarized by descriptive statistics as well as the presentation of concentration vs. time plots based on the PK set. In the analysis of the PK profiles geometric means and standard deviations will be presented in addition to the arithmetic means and standard deviations.

The following PK parameter will be derived and presented using a non-compartment model:

- Area under the curve (AUC) and AUC normalized for the administered dose (AUC_{norm})
- FVIII in vivo half-life ($T_{1/2}$)
- Maximum plasma concentration (C_{max})
- Time to reach maximum plasma concentration (T_{max})
- Mean residence time (MRT)
- Volume of distribution (Vd)
- Clearance (CL)
- Incremental in vivo recovery (IVR)

Analysis of variance (ANOVA) will be used in an exploratory sense to assess a possible association between ABO blood type, VWF:Ag, and the FVIII:C half-life of *Wilate*.

Incremental IVR will be calculated from FVIII:C plasma levels measured before injection and peak levels obtained in the 15-min post-injection sample using actual IMP potencies. The results of the IVR assessments over time will be analyzed in summary tables for each time point and their differences to baseline along with 95% CIs for the mean differences.

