8 APPENDICES

8.1 Formulas for derived variables

| Variable | Description |
|---|--|
| Actual potency | Potency of IMP (IU) based on central laboratory measurements of FVIII content by two assay methods: CHR (chromogenic) and OS (one-stage). The analysis of PK and IVR assessment will be based on actual potencies |
| Durations between two dates | Later date minus earlier date plus 1, expressed in days. (Remark: Duration will be 1, if both dates are the same.) |
| Spontaneous annualized bleeding rate (SABR) | Number of spontaneous bleedings (excluding bleedings occurring in surgery periods) between first dose of IMP and Study Completion visit (or last dose of IMP in case completion visit not performed) / time under prophylaxis (days)/365.25 (see prophylactic treatment phase) |
| Total annualized bleeding rate (TABR) | Number of bleedings (excluding bleedings occurring in surgery periods) between first dose of IMP and Study Completion visit (or last dose of IMP in case completion visit not performed) / time under prophylaxis (days)/365.25 (see prophylactic treatment phase) |
| Surgery Phase | Last treatment for surgery – first treatment for surgery + 1 |
| Prophylactic treatment phase | Date of completion visit or date of last treatment with IMP in case completion visit not performed) – (date of first prophylactic treatment after the PK visit) + 1 – Surgery phases |
| Time in study | Date of study completion – date of screening +1 |

| STATISTICAL ANALYSIS PLAN Protocol No: WIL-30 | |
|--|---------------|
| Version Number: 1.2 | Page 25 of 27 |
| Date of Issue: 2019-07-08 | |

| Variable | Description |
|---|---|
| Time under treatment | Date of last treatment – date of first treatment + 1 (average drug consumption data will be calculated relative to time under treatment) |
| AUC | Area under the curve from baseline to infinity $AUC = \sum \left(\frac{(C_n + C_{n+1})}{2} \cdot \Delta t \right) + \frac{C_{last}}{K}$ (C_{last} is the last available measurement) |
| AUC _{norm} | AUC normalized for the administered dose |
| AUMC | Area under the moment curve (from baseline to infinity) $AUMC = \sum \left(\frac{(t_n \cdot C_n + t_{n+1} \cdot C_{n+1})}{2} \cdot \Delta t \right) + \frac{C_{last} \cdot t_{last}}{K^2} + \frac{C_{last}}{K}$ |
| CL | Clearance $CL = \frac{D}{AUC}$ where D is the actual dose administered (see remark above) |
| C ₀ | FVIII concentration before IMP administration |

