| C _{max} | Maximal measured concentration after end of IMP infusion (peak concentration) |
| ED | Exposure day = each calendar day the subject received IMP |
| Incremental recovery (IVR) | $IVR = \frac{(C_{max} - C_0) \cdot BW}{D}$ where BW stands for the body weight in kg and D is the dose according to the actual potency of the FVIII concentrate as described in above |
| Labelled potency | Potency of IMP (IU) based on label of vial (IU). Dosing analyses will be based on labelled potency |
| MRT | Mean residence time $MRT = \frac{AUMC}{AUC}$ |
| Success (for bleeding episodes and surgeries) | Excellent or good efficacy rating |

| | |
|----------------------------------|---------------|
| STATISTICAL ANALYSIS PLAN | |
| Protocol No: WIL-30 | |
| Version Number: 1.2 | Page 26 of 27 |
| Date of Issue: 2019-07-08 | |

| Variable | Description |
|-----------|--|
| $T_{1/2}$ | In vivo half-life using linear regression on the terminal phase of the logarithm of the concentration; $T_{1/2} = \frac{\ln(2)}{K}$ (where K , the elimination rate constant, is determined as the slope of the regression line) |
| T_{max} | Time to reach maximum plasma concentration (Timing starts at end of infusion) |
| Vd | Volume of distribution $Vd = CL \cdot MRT$ |

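### SAP 8.1 subtracts the pre-dose FVIII level for IVR but not for AUC, half-life or clearance; a level above zero lowers CL by up to about 5%, and only a near-constant endogenous level lengthens T1/2 materially

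*SAP*

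**What the plan says.** Protocol 3.1.1 makes the PK profile the primary endpoint: "The PK profile is based on the following baseline PK parameters for FVIII:C", followed by AUC, T1/2, Cmax, Tmax, MRT, Vd, CL and IVR.

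SAP v1.2 section 8.1 gives the formulas. C0 is the "FVIII concentration before IMP administration", and the only formula containing it is IVR = (Cmax − C0)·BW/D. SAP 5.8 agrees: "Incremental IVR will be calculated from FVIII:C plasma levels measured before injection and peak levels obtained in the 15-min post-injection sample". The AUC row ("Area under the curve from baseline to infinity") sums trapezoids of the measured C_n and adds C_last/K. The AUMC row does likewise. T1/2 is obtained by "In vivo half-life using linear regression on the terminal phase of the logarithm of the concentration". CL, MRT and Vd follow from AUC, AUMC and K.

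Protocol 9.2.2 points the same way: "All other PK parameters will be calculated from FVIII:C plasma levels measured at predefined time points using actual IMP potencies". SAP 5.1.2 invokes the PK software only for missing measurements. Neither document states a pre-dose correction for these parameters, or a decision not to make one.

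Two design features limit C0: "Severe hemophilia A (<1% FVIII:C) according to medical history", and dosing "after a washout period of at least 72 hours from their last FVIII injection".

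**The concern.** C0 need not be zero. Severity is taken from the history, and the flow chart schedules no FVIII:C measurement at screening. The washout is the same whatever the previous concentrate, and children stay on that concentrate until the PK Visit. The plan corrects for C0 in IVR, where it is small against a peak near 90%. It does not correct where concentrations are lowest, at 48 h, although that sample has strong leverage on K. IVR and the other primary parameters therefore rest on different concentration bases in one table.

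With about four or five children per age group, one affected child can move a subgroup mean. If no rule is written down, whether to correct becomes a choice made after C0 has been seen.

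**Working it through.** The documents give no expected half-life or clearance, so there is no figure of the plan's own to reproduce. I applied the SAP 8.1 formulas to noise-free profiles.

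**Inputs**
- Level at time 0: 90%. Protocol 5.4.3 gives a rise of 1.5–2.0% per IU/kg, so 50 IU/kg gives 75–100%; 90% lies inside that range.
- Samples at 0.25, 1, 6, 24 and 48 h (Protocol 6.1.2).
- K from the 6, 24 and 48 h samples. This is an assumption, because the SAP does not define the terminal phase.
- True half-life 8, 10 or 12 h (assumption).
- Constant background 0.5% or 0.9%, both below the eligibility limit (assumption).

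**Worked case: true half-life 8 h, constant 0.5%**
- True levels at 6, 24 and 48 h: 53.514, 11.250, 1.406. Measured: 54.014, 11.750, 1.906, with logs 3.9892, 2.4639, 0.6450.
- Mean time is 26 h, deviations −20, −2, +22, sum of squares 888.
- K = (20×3.9892 + 2×2.4639 − 22×0.6450)/888 = 0.0794 per h.
- T1/2 = 0.6931/0.0794 = 8.73 h, or +9.1%.
- AUC = 1209.1 against 1177.3 without background, or +2.7%. CL = D/AUC, so it falls by 1 − 1177.3/1209.1 = 2.6%.

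**Constant endogenous level, all cases**

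| Background | True T1/2 | Estimated T1/2 | AUC | CL |
|---|---|---|---|---|
| 0.5% | 8 h | 8.73 h (+9.1%) | +2.7% | −2.6% |
| 0.5% | 10 h | 10.50 h (+5.0%) | +2.4% | −2.3% |
| 0.5% | 12 h | 12.40 h (+3.4%) | +2.2% | −2.1% |
| 0.9% | 8 h | 9.25 h (+15.6%) | +4.9% | −4.7% |
| 0.9% | 10 h | 10.88 h (+8.8%) | +4.3% | −4.1% |
| 0.9% | 12 h | 12.72 h (+6.0%) | +3.9% | −3.8% |

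Varying recovery over 1.5–2.0 puts the 0.9%, 8 h case at +14% to +18%. The SAP 2.4 schedule, which has an extra 9 h sample, takes it to +20% at most.

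**Residual previous product**
- Plausible size: dose × recovery × 2^(−72/half-life). With 40 IU/kg (assumed; the top of the *Wilate* prophylaxis range) and recovery 1.5–2.0, C0 is 0.12–0.16% at 8 h, 0.41–0.54% at 10 h, 0.94–1.25% at 12 h and 2.15–2.87% at 15 h.
- Decaying at the same rate as *Wilate*: the log slope is unchanged, so T1/2 shifts by 0.0%. A C0 of 0.5%, 1.5% or 3% lowers CL by 0.5%, 1.6% or 3.2%.
- C0 of 1.5–3% decaying with a 12–14 h half-life: T1/2 shifts by 0 to +4%, AUC rises by about 2–5%.
- C0 of 1.5–3% decaying faster (8 h against a true 10 or 12 h): T1/2 shortens by 0.3–0.8%.

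**What each correction does**
- Subtracting C0·exp(−K·t) with the fitted K removes the AUC and CL error for same-rate residual. It leaves T1/2 where it was: with a constant 0.5% at 8 h, T1/2 stays at +9.1% and the AUC excess falls only from 2.7% to 2.1%.
- Subtracting a constant C0 restores T1/2 and CL exactly when C0 is endogenous. When C0 is same-rate residual it over-corrects. At C0 0.5%, T1/2 becomes −10.8%, −5.3% and −3.5% for true 8, 10 and 12 h. At C0 1.5%, it is −17% at 10 h, and at 8 h the 48 h value turns negative, so its log does not exist.

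MRT and Vd also move. I do not size them, because they depend in addition on the AUMC tail as printed in 8.1, which is a separate matter.

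**The case against.** The strongest reply is that the design keeps C0 small. Children must have severe disease and must be off FVIII for at least three days. With 40 IU/kg and an 8–10 h half-life throughout, the residual is only 0.12–0.54%. The analysis is descriptive, no threshold exists for a shift of a few percent to cross, and the documents give no quantification limit. If that limit is near 1% (an assumption), the 0.5% case could never be corrected. All of this stands, and it bounds the size of the problem. It does not supply the missing rule.

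A second reply is that no single correction is right, because one pre-dose sample cannot separate endogenous from residual FVIII. That also stands, and it is why the fix gives a range.

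Third, the protocol available is version 02, for Ukraine only. SAP v1.2 also cites version 03, so the washout and eligibility terms are unverified for children treated under that version.

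A reader might infer that any pre-dose FVIII lengthens half-life. The arithmetic does not support this for residual product: at the same decay rate T1/2 is unchanged, and with faster decay it shortens slightly. A reader might also infer that the bias undermines an age comparison the study was built to show. A constant 0.9% in both children would shrink a true 8 versus 10 h difference from 2.0 to 1.6 h. But Protocol 3.3 describes the aim as complementing adolescent and adult data, and age groups are only presented side by side, without a test.

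**Conclusion.** The gap is real and lies in the primary endpoint: C0 is handled for IVR and ignored for AUC, AUMC, T1/2, MRT, CL and Vd. With C0 above zero, CL is biased low from either source. The bias is 2–5% for a constant 0.5–0.9% or a residual of 1.5–3%, and under 1% for a residual near 0.5%. T1/2 is materially affected only by a roughly constant endogenous level: about 3–9% at 0.5% and 6–16% at 0.9%, largest in the fastest clearers. Residual product moves T1/2 by about −1% to +4%.

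These sizes rest on assumed half-lives, a one-compartment profile, a three-point terminal fit and an assumed prior dose. If C0 is below quantification in every child, nothing changes. The documents do not show that C0 will be quantifiable in any child, so this is a modest bias left unaddressed, not an established error in the results.

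**What to change.** Amend SAP 5.8 and 8.1, for children with quantifiable C0 (stating the assay limit that defines this):

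1. Report AUC, AUMC, CL, MRT and Vd after subtracting C0·exp(−K·t), and say that this does not alter K or T1/2.
2. As a sensitivity analysis, only where C0 is below 1% and so compatible with an endogenous level, recompute K, T1/2 and the dependent parameters after subtracting a constant C0. Say that this over-corrects if C0 is residual product.
3. Show the uncorrected values beside both. List each child's C0, with the previous product and the time since the last FVIII injection where recorded.

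The cost is SAP wording, a few lines of programming and one extra set of PK tables. The pre-dose sample is already scheduled. Protocol 7.1.2 collects FVIII dosing over the previous six months but does not list the hour of the last injection, so that column may be incomplete. The outcome is a range for each affected child, not one corrected value.

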5 STATISTICAL ANALYSES

All statistical analyses will be performed using SAS[®] for Windows (Version 9.3 or later).

Descriptive statistics will always be given for the entire population.

| | |
|---|---------------|
| 
STATISTICAL ANALYSIS PLAN Protocol No: WIL-30
 | |
| Version Number: 1.2 | Page 16 of 27 |
| Date of Issue: 2019-07-08 | |

The analysis of safety will be based on the SAF set.

Analysis of the PK properties of *Wilate* will be based on the PK set.

For secondary endpoints, FAS and PP analyses will be carried out, unless these analysis sets differ by no more than 1 patient from the FAS.

Analysis of the efficacy and safety of *Wilate* in surgeries will be based on the SURG set.

If not stated otherwise the following standard descriptive statistics will be presented:

Descriptive statistics for continuous data

Number of subjects (N), arithmetic mean, standard deviation (SD), minimum, lower quartile, median, upper quartile and maximum will be presented. Usually mean and quartiles will have 1 decimal more, SD 2 decimals more than the original values (as given with min, max); N has no decimals. These descriptive statistics will be determined for measured values and for differences to baseline.

Descriptive statistics for categorical data

Absolute frequencies (N) will be presented with 0, relative frequencies (%) with 1 decimal. For changes from baseline, shift tables may be generated.

Inferential statistics

If not stated otherwise all statistical tests will be performed as described in the corresponding sections below.

All p-values will be rounded to 4 decimals (p<0.0001 will be displayed, if the p-values are less than 0.0001). Statistical significance will be declared if the rounded p-value will be less than 0.05.

All confidence intervals (CI) will be derived two-sided and at a confidence probability of 1- α = 0.95.

Listings

All subject data will be listed by subject. Identification variable will be the subject ID (composed of study, center and subject number separated by a hyphen, e.g. '30-01-01'). Any derived data listed will also be stored permanently and will be calculated as outlined in section 8.1 of this SAP.

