5.1.2 Missing data

In case of missing weight documentation data will be imputed using the Last Observation Carried Forward (LOCF) approach to calculate the dose per kg body weight (IU/kg). For calculation of PK parameters, missing measurements on a subject's PK profile will be handled according to the algorithms included in the PK software WinNonlin (version 7.0).

No further imputations for missing data will be performed.

Calculations pertaining to the derivation of annual bleeding rates will be based on documented time periods only.

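### SAP 8.1 calls K the elimination rate constant but derives it as the regression slope, which is negative; a minus sign is missing (minor)

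*SAP*

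**What the plan says.** The protocol (3.1.1) states: "The primary endpoint of this study is the PK profile of" Wilate. It lists AUC, AUCnorm, T1/2, MRT, Vd and CL among the parameters that make up that profile.

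SAP v1.2 section 8.1 gives the formulas:

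- T1/2 is described as "In vivo half-life using linear regression on the terminal phase of the logarithm of the concentration", with T1/2 = ln(2)/K.
- K is then described in the same row: "the elimination rate constant, is determined as the slope of the regression line". No minus sign or absolute value appears.
- AUC is the "Area under the curve from baseline to infinity": a linear trapezoid sum plus C_last/K.
- CL = D/AUC, MRT = AUMC/AUC and Vd = CL·MRT, so each depends on K through AUC.

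The K wording is the same in SAP v1.0, v1.1 and v1.2, although v1.2 revised other rows of this table.

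Section 5 (Listings) makes the table binding: "Any derived data listed will also be stored permanently and will be calculated as outlined in section 8.1 of this SAP". WinNonlin is named in section 5.1.2, where the task given to it is the handling of missing measurements on a PK profile.

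**The concern.** The T1/2 row contradicts itself. By its label K is positive; by its derivation K is negative, because the log-concentration line slopes downward. A formula table that section 5 designates as the source for derived data should give the right answer when followed as printed, and this row does not.

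Two results go wrong under a literal reading. T1/2 comes out negative in every child. The extrapolated tail is subtracted from AUC, so AUC and AUCnorm are too low, CL is too high, and MRT and Vd are distorted. The first error is obvious in any output. The second leaves a positive AUC of plausible size.

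**Working it through.** The documents state no half-life or AUC value, so there is no figure of the plan's own to reproduce. The check applies the section 8.1 formulas to a noise-free profile, once with K = slope and once with K = −slope.

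**Inputs from the documents**
- Dose 50 IU/kg (protocol 5.4.1).
- Recovery 2.0% per IU/kg, the upper end of the range in protocol 5.4.3, giving a starting level of 50 × 2.0 = 100%.
- Samples at 0.25, 1, 6, 24 and 48 h (protocol v02, 6.1.2: 15 minutes, then "1 h (±5 min), 6 h (±30 min), 24±2 h, and 48±2 h after the end of injection").
- Linear trapezoid plus C_last/K (SAP 8.1).

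**Assumptions**
- Mono-exponential decline, zero pre-dose level, concentration back-extrapolated to time 0.
- Natural logarithm, slope taken from the last three samples.
- True half-life of 6 to 15 h.

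**Worked case, assumed half-life 10 h**

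The concentrations at 0, 0.25, 1, 6, 24 and 48 h are 100, 98.28, 93.30, 65.98, 18.95 and 3.59%.

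Trapezoid sum = 24.79 + 71.84 + 398.20 + 764.30 + 270.43 = 1529.6 %·h.

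The fitted slope is −ln(2)/10 = −0.0693 per h. The size of the tail is 3.59/0.0693 = 51.8 %·h.

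- K = slope: T1/2 = ln(2)/(−0.0693) = −10.0 h; AUC = 1529.6 − 51.8 = 1477.8 %·h; CL = 50/1477.8 = 0.0338.
- K = −slope: T1/2 = +10.0 h; AUC = 1529.6 + 51.8 = 1581.3 %·h before rounding of the terms; CL = 50/1581.3 = 0.0316.

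AUC ratio = 1477.8/1581.3 = 0.935, a loss of 6.5%. CL ratio = 1581.3/1477.8 = 1.070, an excess of 7.0%.

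**Over the assumed half-lives**

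| Assumed T1/2 (h) | T1/2 with K = slope (h) | Tail size (%·h) | AUC, K = slope | AUC, K = −slope | AUC error | CL error |
|---|---|---|---|---|---|---|
| 6 | −6 | 3.4 | 1024.8 | 1031.5 | −0.7% | +0.7% |
| 8 | −8 | 18.0 | 1272.1 | 1308.1 | −2.8% | +2.8% |
| 10 | −10 | 51.8 | 1477.8 | 1581.3 | −6.5% | +7.0% |
| 12 | −12 | 108.2 | 1638.1 | 1854.5 | −11.7% | +13.2% |
| 15 | −15 | 235.5 | 1795.8 | 2266.8 | −20.8% | +26.2% |

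**Sensitivity.** A recovery of 1.5 instead of 2.0 rescales every concentration and leaves the percentages unchanged. Adding the 9 h sample shown in the SAP flow chart changes the AUC error at 10 h from −6.5% to −6.7%.

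**The case against.** The strongest reply is that the row settles its own sign. It names K the elimination rate constant and uses it for a half-life, and the AUC row adds C_last/K to reach infinity. All of this makes sense only for K > 0, so a competent programmer would read the slope as its size. That stands as evidence of intent and is the main reason the point is minor. It does not make the printed derivation correct.

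A reader might infer that the AUC and clearance results will be wrong without anyone seeing it. The documents do not support that. Section 8.1 defines one K, which feeds both T1/2 and the tail. A literal K makes a listed primary-endpoint parameter negative in every child, and section 6 has the trial statistician check outputs for consistency and plausibility. Correcting K corrects the tail as well. The AUC error survives only if someone repairs the sign inside the T1/2 line and leaves K as it was. That is possible, but the SAP does not prescribe it.

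A reader might also infer a further 2.30-fold error from the unstated base of the logarithm. The ln(2) printed in the same row already implies the natural logarithm, so this is only a wording gap to close.

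Finally, WinNonlin may in practice compute these parameters. Section 5.1.2 says that missing measurements "will be handled according to the algorithms included in the PK software WinNonlin (version 7.0"). This suggests that the parameters are not simply hand-coded from the table, but what it delegates is missing measurements, so it does not formally replace section 8.1.

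**Conclusion.** Wrong as written, low practical weight: minor. The contradiction between the label and the derivation of K needs no assumption beyond a falling terminal concentration, and neither does the negative half-life that a literal reading gives.

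The size of the AUC and CL error does rest on assumptions: half-lives that the documents do not give, mono-exponential decline and a last sample at 48 h. It grows with half-life, because more of the area then lies beyond 48 h. These figures describe what literal use would do; they are not a forecast of the reported results.

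**What to change.** In the T1/2 row of SAP 8.1, replace the description of K with: *K = minus the slope of the least-squares line of the natural logarithm of concentration on time over the terminal phase.* Keep T1/2 = ln(2)/K and the tail C_last/K as they are.

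Make the change together with the separate correction of the AUMC row. That tail is printed as C_last·t_last/K² + C_last/K; the standard form is C_last·t_last/K + C_last/K². Correcting the sign of K alone would leave MRT and Vd wrong, and correcting the exponents alone would leave T1/2 and AUC wrong.

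The cost is one line of SAP text for K, with no effect on data, patients or design.
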